1.0 Table of Contents

1.0	7
2.0	7
3.0	7
4.0	7
5.0	8
6.0	12
7.0	12
8.0	12
9.0	12
10.0	13
11.0	13
12.0	14
13.0	14
14.0	16
15.0	16
16.0	17
17.0	17
18.0	18
19.0	18
20.0	18
21.0	19
22.0	19
23.0	20
24.0	20

PROTOCOL TITLE: Prospective Randomized controlled study comparing liposomal bupivacaine to bupivacaine interscalene blocks for arthroscopic rotator cuff repair surgery

VERSION DATE: 8/5/11/2020

ABBREVIATIONS/DEFINITIONS

- LB/ liposomal bupivacaine
- RCR/rotator cuff repair
- QOR/Quality of Recovery
-

PROTOCOL TITLE: Prospective Randomized controlled study comparing liposomal bupivacaine to bupivacaine interscalene blocks for arthroscopic rotator cuff repair surgery

VERSION DATE: 8/5/2020

STUDY SUMMARY

Study Title	Prospective Randomized controlled study comparing liposomal bupivacaine to bupivacaine interscalene blocks for arthroscopic rotator cuff repair surgery
Study Design	Prospective randomized double blind study
Primary Objective	Total opioids in 72 hours
Secondary Objective(s)	Pain scores within 72 hours, QOR at 72 hours, Number of phone calls to surgeon, adverse events, time to discharge
Research Intervention(s)/Investigational Agents	Liposomal bupivacaine and bupivacaine vs bupivacaine
Scientific Assessment	HRPP facilitated scientific assessment
IND/IDE # (if applicable)	Study Medication has been approved for use in shoulder surgery April 6, 2018
IND/IDE Holder	n/a
Investigational Drug Services # (if applicable)	n/a
Study Population	Adult patients aged 18 and older who are undergoing arthroscopic rotator cuff repair surgery
Local Sample Size (number of participants recruited locally)	90

PROTOCOL TITLE: Prospective Randomized controlled study comparing liposomal bupivacaine to bupivacaine interscalene blocks for arthroscopic rotator cuff repair surgery

VERSION DATE: 8/5/2020

2.0 Objectives

Purpose: **To determine if LB plus bupivacaine provides superior pain control compared to bupivacaine alone when injected in an interscalene block for patients undergoing arthroscopic rotator cuff repair surgery.**

2.1

3.0 Background

- 3.1 Significance of Research Question/Purpose: LB has not been adequately studied in peripheral nerve blocks. One study has been done in RCR surgery and showed superior analgesia compared to bupivacaine.
- 3.2 Preliminary Data: It is our standard of care to use this medication in an interscalene block at the U of MN for patients undergoing RCR. A retrospective study performed showed superior analgesia and less opioids for those who had LB plus bupivacaine.
- 3.3 Existing Literature: Vandepitte et al showed that LB plus bupivacaine was superior to bupivacaine when used in interscalene nerve block for patients undergoing major shoulder surgery (both RCR and TSA).

4.0 Study Endpoints/Events/Outcomes

- 4.1 Primary Endpoint/Event/Outcome: To determine if LB plus bupivacaine in an interscalene block results in less opioid use over 72 hours compared to bupivacaine only for RCR surgery.
- 4.2 Secondary Endpoint(s)/Event(s)/Outcome(s):
 - To determine if LB plus bupivacaine in an interscalene block results in less pain over 72 hours as compared to bupivacaine only in an interscalene block for RCR surgery. Assessed via total pain scores
 - To determine if LB plus bupivacaine in an interscalene block results in improved QOR at 72 hours as compared to bupivacaine only in an interscalene block for RCR surgery. Assessed via QOR 15 patient survey.
 - To determine if LB plus bupivacaine in an interscalene block results in fewer phone calls to the surgeon within 72 hours as compared to bupivacaine only in an interscalene block for RCR surgery.
 - To determine if LB plus bupivacaine in an interscalene block hastens readiness for hospital discharge compared to bupivacaine only in an interscalene block for RCR surgery. Study Intervention(s)/Investigational Agent(s)
- 4.3 Description: LB is a long acting local anesthetic. It is liposome encapsulated bupivacaine which allows for prolonged release of bupivacaine over a 72

PROTOCOL TITLE: Prospective Randomized controlled study comparing liposomal bupivacaine to bupivacaine interscalene blocks for arthroscopic rotator cuff repair surgery

VERSION DATE: 8/5/2020

hour period. Bupivacaine is a medium acting local anesthetic which provides between 6 and 24 hours of analgesia when used in a peripheral nerve block. Both medications are standard of care for use in interscalene blocks here at the U of MN. Acetaminophen is a medication used to treat pain, gabapentin is a gabapentinoid which is used to treat postoperative pain.

4.4 Drug/Device Handling: The LB will be stored in a locked pyxis fridge in a box labeled study LB. It will be retrieved by the PI and sub I's for use in the interscalene blocks.

- The LB will be stored in a locked pyxis fridge in a box labeled Liposomal Bupivacaine. The anesthesiologists in charge of regional anesthesia the day the procedure will be informed will write the order for dispensing the medication and the block per standard of care. It will be retrieved by the PI and sub I's for use in the interscalene blocks.

4.5 Biosafety: n/a

4.6 Stem Cells: n/a

5.0 Procedures Involved

5.1 Study Design: **Level I randomized prospective outcomes study comparing two groups of patients. One group will receive LB plus bupivacaine for an interscalene block. The other will receive bupivacaine for an interscalene block injection.**

Study Procedures: Patients will be identified in the pre-operative time period by the surgeons and if possible will be consented by the research coordinator or research assistant. If that is unable to be accomplished the patient will be introduced to the study and given a copy of the consent form to evaluate prior to surgery. On the day of surgery, the research coordinator, research assistant or primary or sub investigators will determine if the patient has any questions so that they can be answered. After discussion with the person obtaining consent, consent will be obtained in the pre-operative area. A random number generator will be used to determine if the patient will have LB plus bupivacaine or bupivacaine for their interscalene block. The primary investigator will access the number generator in the pre-op area immediately prior to block placement. The website www.random.org will be used as the random number generator.

Treatment technique:

All patients will receive preoperative oral multimodal medications consisting of acetaminophen 975 mg and gabapentin 300 mg.

After completion of the preoperative process the patient will be placed in the supine position with the head of the bed elevated 30 degrees with standard ASA monitors applied. Sedation will be provided with midazolam 0-2 mg and propofol 50 mg. The

PROTOCOL TITLE: Prospective Randomized controlled study comparing liposomal bupivacaine to bupivacaine interscalene blocks for arthroscopic rotator cuff repair surgery

VERSION DATE: 8/5/2020

interscalene groove will be identified with the ultrasound. Using sterile technique, a 21g Nerve block needle will then be inserted and advanced under ultrasound guidance until it is in the interscalene groove. Once in the interscalene, 20 mL of local anesthetic will be injected, with 10 mL deposited at the top of the brachial plexus and 10 mL at the bottom. In the study group, 5 mL of each 0.5% bupivacaine and LB will be injected at each location. The control group will have 20 mL of 0.5% bupivacaine divided between the injection sites (10 mL at each site). The patient will be monitored in the preoperative area until he/she is brought into the operating room for their procedure. A working block prior to surgery will be confirmed via sensory testing of the shoulder.

All patients will undergo a standard induction with propofol 1.5-3.0 mg/kg, ondansetron 4 mg, dexamethasone 10 mg and ketamine 0.25 mg/kg. A MAC or general LMA or ETT will be placed and an opioid sparing technique will occur. Standardized maintenance will be a propofol infusion without neuromuscular blockers. 25-50 mcg of IV Fentanyl will be utilized for increases in heart rate greater than 20% or increases in systolic blood pressure above baseline.

Once in the operating room the surgeon will use an additional 10 mL of 0.25% bupivacaine for skin, subcutaneous, and intraarticular injection.

When the operation is complete, the patient will be woken up and brought to the PACU. There the patient will receive IV fentanyl for a pain score of greater than 7 (50 mcg of Fentanyl x 2 if needed). If more than 100 mcg of fentanyl is given and pain still remains above a 7 then IV hydromorphone will be used (max dose of 1 mg and given in increments of 0.3 mg q 10 minutes prn severe pain). Once the patient is able to tolerate oral medications a dose of 5 mg of oral oxycodone (or 2 mg of oral hydromorphone if allergic to oxycodone) will be given if their pain score is greater than 4 (on the Visual Analog Scale). Once the patient meets discharge criteria, they will be discharged home where each day they will fill out a pain diary. Additionally, a member of the research team will call the patient for signs of complications and ask the patient their current pain score, total opioid pills taken and non-opioid pain medication taken at 24, 48, and 72 hours postoperatively. Additionally, they will perform a Quality of Recovery Score survey at 72 hours, and 14 days postoperatively. An Ultrasound of the diaphragm will be completed by a blinded anesthesiologist in the PACU to assess diaphragm function. All patients will be discharged with instructions to take acetaminophen 975 mg q8 hours & ibuprofen 600 mg q6 hours. Additionally they will have opioid pain medication to take as needed for pain greater than 4. They will either have hydromorphone 2mg, 30-40 pills, with dosing being 1-2 pills q4 hours prn severe pain. Or they will have a prescription for oxycodone 5 mg, 30-40 pills, dosing 1-2 pills q 4 hours prn severe pain.

Enrollment procedures: Patients will be identified in the pre-operative time period by the surgeons and if possible will be consented by the research coordinator or research assistant. If that is unable to be accomplished the patient will be introduced to the study

PROTOCOL TITLE: Prospective Randomized controlled study comparing liposomal bupivacaine to bupivacaine interscalene blocks for arthroscopic rotator cuff repair surgery

VERSION DATE: 8/5/2020

and given a copy of the consent form to evaluate prior to surgery. On the day of surgery, the research coordinator, research assistant or primary or sub investigators will determine if the patient has any questions so that they can be answered. After discussion with the person obtaining consent, consent will be obtained in the pre-operative area. Subjects interested in the study will be presented with consent and Health and Insurance Portability and Accountability Act (HIPAA) forms. The patient will review the forms with the surgeon, research staff, or anesthesiologist. Subjects will be reminded that participation is completely voluntary, and that they may stop participation at any time without question or penalty. The surgeon, research staff, or anesthesiologist will answer any questions that the subjects may have about the study. If the patient decides to participate, they will be asked to sign the consent and HIPAA forms. One copy will be saved for study records, and the subject will be provided with a copy of the forms for their own records. The patient will then have an opportunity to ask any questions of the surgeon regarding the treatment option that has been selected. All forms will be locked and stored in a file cabinet in the research department. Enrollment will proceed from July 2018 to July 2019. Enrolling consecutive patients will help reduce selection bias.

Assessments: Post-operatively patients will be evaluated at 2 and 6 hours post-operatively by a blinded research staff. This person will not be aware of the patient's mode of analgesia. The patients will be contacted via in person assessment or via telephone at 24, 48, and 72 hours +/- 5 hours. Patients will be asked to rate their pain on scale of 0-10. The amount of opioids used by the patient will be recorded as will any other adjuvant pain medication used. The time in phase 1 and phase 2 of PACU will be recorded. The patients will be asked at 72 hours post-injection if they would undergo interscalene block with their medication again or if they would opt for a different form of pain management. Patients will fill out a Quality of Recovery Survey at 72 hours and 14 days, and be assessed for block related complications at this time. All complications will be recorded including:

- Failure of the block
- Wound infections
- Subsequent procedures
- Complications related to placement of the interscalene block including nerve injury, prolonged sensory loss greater than 3 days, prolonged arm weakness greater than 3 days
- Opioid related side effects of nausea and/or vomiting
- Local anesthetic toxicity as evidenced by seizures or cardiovascular collapse without other reasonable etiology

Patients will be asked in the daily phone call if they or their family contacted anyone (any health care professional) regarding their pain overnight and that will be documented.

All data will be recorded on the Clinical Diagnostic Sheet and will then be given to the research coordinator for manual data entry. Data collection will continue until POD #14. At that time study participation will be terminated. Should patients be re-admitted to the

PROTOCOL TITLE: Prospective Randomized controlled study comparing liposomal bupivacaine to bupivacaine interscalene blocks for arthroscopic rotator cuff repair surgery

VERSION DATE: 8/5/2020

hospital in the next two weeks (Up to POD #30) for pain, a notation will be made in study records.

An analysis of the total cost of analgesics will be tabulated at the conclusion of the study to determine the most cost effective treatment option as this will be added into the cost of hospitalization including the number of days each patient spent in the hospital.

Blinding Procedure: The research assistant in this study will be blinded to the method of analgesia for the patient. The research assistant will assess pain one time per day. This person will not be responsible for any clinical testing and will record all data in the protected database daily. They will not have any access to the patients' clinical records or chart. **Any questions from the patient will be referred to the on-call resident or staff on call.**

5.2

Describe:

- The interscalene block is standard of care for patients and would be performed regardless of patient's participation in the study. All patients still would get preoperative multimodal treatment as well as an opioid sparing anesthetic.
- Patients would be required to take a dose of acetaminophen 975 mg oral and gabapentin 300 mg oral prior to surgery. They would then be required to receive an interscalene block with either liposome bupivacaine and bupivacaine or bupivacaine. Intraoperatively they would be required to receive propofol, lidocaine, ondansetron, dexamethasone, and ketamine for induction of anesthesia.
- In addition to the surveys used to measure subjective and objective outcome, other data will be collected during patient interviews including:
 - Demographic data
 - Age
 - Weight
 - ASA class
 - Duration of surgery
 - Pain Score at 2, and 6 hrs after surgery and once a day thereafter
 - Length of stay in recovery room both phase 1 and phase 2
 - Amount of opioids given intraoperatively and post-operatively
 - Satisfaction with treatment
 - Quality of recovery survey at 72 hours and 14 days
 - Non opioids used
 - Adverse events
 - Length of hospital stay

PROTOCOL TITLE: Prospective Randomized controlled study comparing liposomal bupivacaine to bupivacaine interscalene blocks for arthroscopic rotator cuff repair surgery

VERSION DATE: 8/5/2020

- 5.3 Study Duration: We anticipate the study to take from June 2018 to June 2019. Patients will be in the study for 14 days and then their chart monitored for up to 30 days post surgery. The data analysis should take one month after full enrollment of the study.
- 5.4 Individually Identifiable Health Information: This study involves the use of individually identifiable health information. Please see attached HIPAA authorization form.
- 5.5 Use of radiation: n/a
- 5.6 Use of Center for Magnetic Resonance Research: n/a

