12.0 Withdrawal of Participants

12.1 Withdrawal Circumstances: Subjects who have consented prior to the day of surgery and for some reason choose not to participate will be withdrawn and a notation will be made in the study records and these people will be considered screen failures. The surgeon may choose to withdraw the patient from the study prior to surgery for any medical reason or if they suffer a major life threatening adverse event.

12.2 Withdrawal Procedures: If the patient is withdrawn from study prior to the procedure, they will be noted in study records as screen failures. If they undergo the procedure and they decide they no longer want to be a part of the study or withdrawn by the physician, they will be withdrawn and no further data will be collected. This will also be noted in the study documentation.

12.3 Termination Procedures: If the study is terminated for any reason, or there is more than 5 % major adverse events the data that is already collected will be stored in a secure location only accessible to research personnel on this study. No further data will be collected if the study is terminated.

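### As written, an already allocated patient can be recorded as a screen failure, because the cut-off in Section 12.2 falls after an unrecorded random draw

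*Combined protocol and SAP*

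**What the plan says.** **Allocation (Section 5.1).** "The website www.random.org will be used as the random number generator". On who draws and when: "The primary investigator will access the number generator in the pre-op area immediately prior to block placement". The section gives no rule linking numbers to arms, no log of the draw and no statement that the first number stands. The allocated arm is not among the data items listed in Sections 5.2 and 6.2.

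**Drug handling (Section 4.4).** Of the liposomal bupivacaine (LB) the plan says: "It will be retrieved by the PI and sub I's for use in the interscalene blocks". The regional anesthesiologists on duty "will write the order for dispensing the medication and the block per standard of care".

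**After the draw (Section 5.1).** Once the block is placed: "The patient will be monitored in the preoperative area until he/she is brought into the operating room for their procedure". Then: "A working block prior to surgery will be confirmed via sensory testing of the shoulder". No consequence is attached to that test.

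**Withdrawal (Sections 12.1 and 12.2).** "The surgeon may choose to withdraw the patient from the study prior to surgery for any medical reason", or after a life-threatening adverse event. On status: "If the patient is withdrawn from study prior to the procedure, they will be noted in study records as screen failures". For anyone withdrawn after the procedure, by their own choice or by the physician, Section 12.2 ends data collection.

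**Analysis (Section 15).** No analysis population is defined. The statistician is to work from the protocol.

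**The concern.** A randomised comparison is protected only if the allocation is fixed once made and every allocated patient stays in the count. Here an investigator makes the draw, and the same small group fetches the LB, so someone involved knows the arm before the injection. No record of the draw is described, and a patient withdrawn after it may be labelled a screen failure. That label normally means a person who was never randomised. A reader of the final report could not tell whether screen failures arose before or after allocation, or in which arm.

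If removals after the draw were related to the arm, or to how well the block worked, the opioid comparison would be biased. Removals unrelated to either would cost patients but would not bias the result.

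**Working it through.** **1. Order of events.** From Section 5.1: consent, draw, block, sensory test and monitoring, operating room. Section 12.2 does not define *procedure*. If it means the block, the gap after the draw is short. If it means the operation, which is how Section 5.1 uses the word when the patient goes to the operating room, the gap also includes the block and its test. The draw comes first on both readings, so the cut-off does not exclude an allocated patient on either.

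**2. The plan's own figures.** Section 10.1 has 90 consented with 20% loss. With the target of 70 from Section 15.2, 70 / (1 − 0.20) = 87.5, so 88, which is close to 90. Section 23.0 instead treats 90 as screened and 70 as enrolled. The plan therefore leaves open whether the roughly 20 losses (90 − 70) fall before or after allocation, and the cut-off is what would settle it.

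**3. Size of a given shift.** Assumptions, not in the documents: 35 per arm, no true effect, two-sided 5% test. For a bias of δ standard deviations,

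type I error ≈ Φ(−1.96 + δ√(35/2)) + Φ(−1.96 − δ√(35/2)), with √(35/2) = 4.183.

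- δ = 0.05: 0.05 × 4.183 = 0.209, giving 5.5%.
- δ = 0.10: 0.10 × 4.183 = 0.418, giving 7.0%.

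A shift of this size would arise if patients with failed blocks were dropped, the failure rates differed by 5 to 10 percentage points, and a failed block added 1 SD of opioid use: 0.05 × 1 to 0.10 × 1. All three are assumptions.

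**4. Redraws and removals by simulation.** Outcome Y = ρX + √(1 − ρ²)e, where X is the impression of likely opioid use held by the person drawing or removing, and ρ is 0.3 or 0.5 (assumed). 70 patients are analysed. Each range runs from ρ = 0.3 to ρ = 0.5.

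| Assumed behaviour | Type I error |
|---|---|
| Removals on X by someone who does not know the arm, 10 or 20 patients | 5.0–5.1% |
| Redraw until favourable in 10% of patients | 5.4–6.3% |
| Redraw until favourable in 30% of patients | 9.2–16.8% |
| At most one redraw, in 30% of patients | 6.0–7.8% |
| Arm known, 10 removed at random among unfavourable draws | 6.0–8.0% |
| Arm known, the 20 most unfavourable removed | 16.2–37.9% |

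The rows for redrawing until favourable agree with a closed form. If a share f of patients is steered, the bias is f × ρ × 2√(2/π) = 1.596 fρ. For f = 0.3 and ρ = 0.5 that is 0.24 SD, and the formula in step 3 then gives 17.0%.

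**5. What is left to protect.** Section 5.1 ends enrolment in July 2019, this version is dated August 2020, and Section 15.2 speaks of continuing to 70. The number remaining is not stated. If only the last m patients were open to redraws at the 30% rate, type I error would be 5.0–5.3% for m = 10, 5.3–5.8% for m = 20 and 6.0–7.7% for m = 35.

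**The case against.** The strongest reply is that the live draw is unpredictable, enrolment is consecutive, and Section 12.2 has withdrawals noted in study records. All three are true. None of them keeps an allocated patient in the count, and the note is not required to state the arm.

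Three stronger readings are tempting, and the documents do not support them.

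- **That allocations were redrawn or patients selectively removed.** Nothing in the documents suggests it. The gap is in what the plan would allow and record.
- **That the surgeon removes patients according to their arm.** No passage says the surgeon learns the arm. The screen failures in Section 12.1 are patients who consented before the day of surgery and then chose not to take part. The surgeon's stated grounds are medical, including a life-threatening event.
- **That patients with failed blocks will be dropped.** Section 5.1 attaches no withdrawal to the sensory test and lists block failure as a complication to be recorded, which points to keeping these patients. Section 12.2 simply does not say so.

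The objection that the large error rates are remote also stands. The 37.9% needs 20 of 90 allocated patients removed by someone who knows the arm and picks the worst.

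Two limits on remedies must be accepted. A log kept by the person drawing would not stop a deliberate redraw, since only the preferred number need be entered. Nor does an LB order reveal the allocated arm: Sections 3.2 and 4.3 describe LB as standard of care at the site, so a patient withdrawn before the block might receive it anyway.

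**Conclusion.** The point holds as a gap in the rules for allocation and status. The screen-failure cut-off follows the draw on either reading, no record of the draw is described, and Section 15 contains nothing that restores an allocated patient to the analysis.

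The effect on the result is unknown and may be nil. On the assumptions shown, type I error is 5.0% if removals are made without knowledge of the arm and about 5.5 to 7.0% for a shift of 0.05 to 0.10 SD. It rises well above that only with frequent redraws or removals by someone who knows the arm. A reader might infer from the higher simulated rates that the trial's error rate is compromised. Those rates rest on assumed misuse, of which the documents show none. The change is worth making because it is cheap, and because without it the report could not show that all allocated patients were accounted for.

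**What to change.** 1. **Section 12.2, status.** Apply *screen failure* only before allocation. Every allocated patient counts as randomised, is reported by arm and is analysed in that arm.
2. **Section 12.2, data collection.** Amend the rule that ends data collection. A physician's withdrawal after allocation, or a failed block, should not stop outcome collection; only the patient's withdrawal of consent to follow-up should. If the operation is cancelled or the patient refuses follow-up, report the outcome as missing, by arm and reason. The clinical grounds for withdrawal do not change.
3. **Section 5.1, patients still to be enrolled.** Replace the live draw with an unblocked 1:1 list prepared by the staff statistician and concealed from the investigators. Sequentially numbered, sealed, opaque envelopes at each of the three surgical locations in Section 21.1 would serve. Each is opened after consent and registration and logged with ID, date and time. The blinded research assistant should not open them. Logging the investigator's first draw would improve the record but is not a substitute.
4. **Patients already allocated.** Keep their allocations. From whatever allocation records exist, list by arm any patient withdrawn after the draw. Do not infer the arm from LB orders alone.

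**Cost.** A short amendment, and preparation of the list and envelopes. No extra patients are needed. Chance imbalance is no worse than with a simple 1:1 draw: for 70 patients the probability of a 40:30 split or worse is 28% in either case. Part 3 helps only the unstated number of patients remaining, and parts 1 and 4 cannot recover outcomes that were never collected.

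### Does counting opioid pills of two possible drugs, at a final call made between 67 and 77 hours, compromise the 72-hour opioid total?

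*Combined protocol and SAP*

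**What the plan says.** The Study Summary gives the primary objective as "Total opioids in 72 hours". Section 4.1 looks for "less opioid use over 72 hours compared to bupivacaine only for RCR surgery". Neither names a unit, a conversion or a time zero.

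Section 5.1 describes where the data come from:

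- **In theatre:** "25-50 mcg of IV Fentanyl will be utilized for increases in heart rate greater than 20" per cent, or for a rise in systolic pressure.
- **In recovery:** IV fentanyl, then IV hydromorphone, then oral oxycodone 5 mg, or oral hydromorphone 2 mg for a patient allergic to oxycodone.
- **At home:** the first option reads "They will either have hydromorphone 2mg, 30-40 pills, with dosing being 1-2 pills q4 hours prn severe pain". The alternative is oxycodone 5 mg in the same quantity and on the same schedule. Patients are "discharged home where each day they will fill out a pain diary".
- **By telephone:** the team will "ask the patient their current pain score, total opioid pills taken and non-opioid pain medication taken at 24, 48, and 72 hours postoperatively". The Assessments paragraph allows 5 hours either side of each contact and says that the amount of opioid used is recorded.

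Section 5.2 lists the amounts of opioid given during and after surgery among the data items. Section 6.2 names Epic as a source alongside the patient. Section 15.3 gives the statistician the protocol as the basis for analysing the objectives. It contains no derivation of the primary variable.

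**The concern.** This is the only primary endpoint, and the telephone question is worded as a number of pills. If those numbers were simply added, two patients with the same opioid intake could receive different values because one took hydromorphone and the other oxycodone. A count taken at 67 hours misses 5 hours of use, and one taken at 77 hours may add 5. The text also does not say whether intraoperative fentanyl enters the total, or from what moment the 72 hours run.

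Two things could be at stake. One is measurement noise that lowers the power of the main comparison. The other is that several totals can be built from the same records, and the protocol does not choose between them. Bias between arms would need drug choice or call timing to differ by arm, and nothing in the documents suggests that.

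**Working it through.** **The plan's own figure.** Section 15.2 states 70 patients for an estimated 80% power, borrowed from another study. It gives no effect size, standard deviation or significance level, so the figure cannot be reproduced. To price the concern I take it at face value and assume 35 per arm and a two-sided 5% t-test. The standardised difference giving 80% power is then d = 0.679.

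**Is a pill count the likely endpoint?** The endpoint wording is opioid use, not pills. Amounts are recorded (section 5.1, Assessments; section 5.2) and Epic is a source (section 6.2). If any IV recovery dose counts, a total in pills is not even possible. The literal pill sum is therefore a worst case.

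**Cost of a literal pill count.** Let r be the number of oxycodone 5 mg pills that equal one hydromorphone 2 mg pill, p the share of patients on hydromorphone (equal in both arms), and c the coefficient of variation (CV) of true use. The count is true need times M, where M = 1 for oxycodone and 1/r for hydromorphone. Then

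CV_total² = (1 + c²)(1 + CV_M²) − 1, inflation = CV_total / c, and power is evaluated at d / inflation.

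The ranges for r (0.8 to 1.6), p (10% to 50%) and c (0.5 to 1.0) are assumptions; the documents state none of them.

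| r | p = 10%: c = 0.5 / c = 1 | p = 50%: c = 0.5 / c = 1 |
|---|---|---|
| 0.8 | 79.0% / 79.6% | 77.6% / 79.0% |
| 1.0 | 80.0% / 80.0% | 80.0% / 80.0% |
| 1.33 | 78.9% / 79.5% | 76.1% / 78.4% |
| 1.6 | 77.4% / 78.9% | 70.2% / 75.9% |

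The worst cell in full: M is 1 or 0.625 with equal probability, so its mean is 0.8125, its variance 0.0352 and CV_M² = 0.0533. With c = 0.5, CV_total² = 1.25 × 1.0533 − 1 = 0.3166, CV_total = 0.563 and inflation = 1.125. The effective difference is 0.679 / 1.125 = 0.604, and power is 70.2%.

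**The documents' only hint about r.** The recovery-room rule replaces oxycodone 5 mg with hydromorphone 2 mg, and both home pills carry the same schedule. Read as an equivalence, 5/2 = 2.5 mg oxycodone per mg hydromorphone, so one 2 mg pill equals 2 × 2.5 / 5 = 1.0 oxycodone pill. The loss is then zero. The protocol does not call this a conversion.

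**Cost of the call window.** 72 − 5 = 67 h, 72 + 5 = 77 h, and 5/72 = 6.9% of the period. Assume a constant rate of use and a count that runs to the moment of the call.

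- Calls spread evenly over 67 to 77 h: CV of observed time = (10/√12)/72 = 0.040; power 79.7% (c = 0.5) or 79.9% (c = 1).
- Half the calls at each end: CV = 5/72 = 0.069; power 79.1% or 79.6%.

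**Cost of narrowing the window.** Confining the last call to 72 to 77 h halves a 10-hour window in a trial expecting 20% loss (section 10.1). One more patient lost per arm (34 against 35) gives 78.8%, a drop of 1.2 points. Evenly spread calls cost 0.1 to 0.3 points, and the extreme split 0.4 to 0.9.

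**The case for a change.** The strongest reply is that recoverable data are not a rule. Home pills only, home plus recovery, or all opioids are each defensible, and section 15.3 sends the statistician to a protocol that does not choose. Section 5.1 also keeps the blinded research assistant away from the chart, so if that person makes the calls the drug cannot be looked up on the spot.

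Some of this stands. The unit, the conversion, time zero and the treatment of intraoperative fentanyl are unstated, and writing them down would be good housekeeping. But the prescription can be linked later by someone with chart access, and conversion to a common opioid unit is routine. Recovery-room doses are postoperative and inside 72 hours, so they fall naturally in the total; only intraoperative fentanyl is clearly open. The 5-hour tolerance says when the contact takes place. The period counted is already 72 hours, and a late call can ask about use up to that point.

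The clinical text of section 5.1 raises two further matters. Two fentanyl doses of 50 mcg make exactly 100 mcg, yet the next step requires that 100 mcg be exceeded. Home opioid is described as "they will have opioid pain medication to take as needed for pain greater than 4" and then as for severe pain, which is not defined. The investigators must reconcile the fentanyl passages and clarify the home wording. Both apply equally to the two arms, have no shown effect on the primary comparison, and do not add to the statistical concern.

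**Conclusion.** No change to the statistical plan follows. The missing unit and conversion are a gap in detail that a competent analyst fills sensibly from data the plan already collects. With drug mix and call timing alike in the two arms, the issue is noise and not bias. Even the unlikely literal pill count keeps at least 77% power when 10% of patients take hydromorphone, and reaches 70% only with half the patients on hydromorphone, a pill ratio of 1.6 and a CV of 0.5 together. The call window costs less than one percentage point, and tightening it could plausibly cost more through lost contacts. These figures rest on the assumed 35 per arm, the stated 80% power, a two-sided 5% t-test, and assumed ranges for the pill ratio, hydromorphone share and variability of use.
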